### **Health System and Societal Outcomes:**

Primary care physician or nurse practitioner encounters: the number of new and repeat primary care physician or nurse practitioner visits for LBP per patient. This measure will be considered a proxy for a potential increase in primary care team capacity achieved if the LBP-related workload of primary care physicians or nurse practitioners is reduced, thus increasing their availability to provide care to other patients.

Healthcare utilization within the primary care team: using data being collected from the EHR: consultations with other primary care team members (e.g., physicians, nurse practitioners, nurses, social workers, and occupational therapists) and group programming accessed within the primary care organization.

Healthcare utilization outside of the primary care team: using self-report data from follow-up surveys cross checked with reports the electronic health record when possible: medications used; walk-in clinic visits; ED visits; inpatient hospital stays; surgeries, injections, and other interventional procedures; visits to specialist physicians; diagnostic imaging; and visits to other health professionals outside the primary care team (e.g., chiropractors, massage therapists, occupational therapists, physiotherapists, chronic pain clinics).

Missed Occupational Activities: using self-report data from follow-up surveys: time (days) lost from paid employment, volunteer, homemaking, or educational activities related to LBP.

Assistance required: using self-report data from follow-up surveys: paid and unpaid assistance required. For example, self-care (e.g., taking medications, dressing/undressing, going to the bathroom, bathing/showering, grooming), shopping/groceries, meal preparation, housework, managing finances, or transportation (e.g., to a medical appointment).

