### **Implementation Measures:**

The following measures will be used to assess how the PT-led primary care model and usual physician- or nurse practitioner-led primary care model were implemented.

**Timely access to LBP care:** using the percentage of patient participants with LBP who are assessed within 48 hours of calling for an appointment. Participants who learned about the study and were invited to participate during an appointment for their LBP will not be included in this analysis.

**PT as the first point of contact:** using the percentage of patient participants with LBP in the PT-led primary care arm who visited a PT as their first point of contact for the current episode of LBP.

**Access to PT services:** using the percentage of patients who are classified as medium or high risk on the STarT Back screening tool who access PT (as endorsed by guidelines).

**LBP management:** using the following data being collected from the EHR to describe the LBP management provided to patient participants in each arm: education; exercise; psychological approaches; referrals to other primary care team members (e.g., primary care physicians, nurse practitioners, nurses, social workers, occupational therapists, group programming); referrals made to health professionals outside of the primary care team; medications prescribed, deprescribed, and suggested; diagnostic imaging ordered; lab work ordered and received; notes to employers or insurers; interprofessional communications with the primary care team; and other interventions provided.

**Patient adherence to recommendations:** adherence to recommendations from the primary care PT is being collected at the 6-week follow-up. For patient participants identified as medium- or high-risk using the STarT Back classification, whether or not they accessed recommended PT (either through a referral to a community PT or through the PT in primary care) is being collected as part of our health utilization survey questions.

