Pain intensity, health-related quality of life (EQ-5D-5L), PSEQ, PCS, TSK-11, and PHQ-2 outcomes will be analyzed as described for the primary outcome, adjusted for the same covariates. Patient satisfaction and global rating of change outcomes have no baseline measures, and will be analyzed using ordinal logistic regression with clusters as random effects, adjusting for the same covariates as described above. When individual items are missing from within any of the questionnaires, we will use simple mean imputation as suggested by Chavance. Serious adverse events will be presented descriptively by arm due to low expected counts. Any adverse events (yes/no) will be presented as incidence rates with confidence intervals and compared by calculating relative risks with confidence intervals from robust Poisson regression using GEE-type robust variance estimators (using *PROC GLIMMIX* with *EMPIRICAL* option in SAS) to account for clustering and using an exchangeable working correlation matrix. We will use empirical covariance (“sandwich”) bias-adjusted (residual-based) estimators and the Fay and Graubard correction to account for small number of clusters in all models comparing incidence rates. In the case of non-convergence or unstable estimates due to the small number of clusters, we would attempt to fit the model using an independent working correlation matrix. Other information related to non-serious adverse events (i.e., severity and duration) will be reported descriptively.

We have planned a secondary analysis, a responder analysis, to compare the proportion of participants who experience a meaningful improvement in disability (RMDQ) in the PT-led primary care model arm versus the usual care arm. We will define a meaningful improvement as an improvement of greater than or equal to 30% improvement on the RMDQ, corresponding to an established minimally important difference among people with LBP. We will calculate the proportion of participants who

experience a meaningful improvement in each arm and compare between groups using robust Poisson regression, with GEE-type robust variance estimators to account for clustering. We will use empirical covariance (“sandwich”) bias-adjusted (residual-based) estimators and the Fay and Graubard correction to account for small number of clusters.

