#### Healthcare utilization and missed occupational activity outcomes

For healthcare utilization and missed occupational activities outcomes, we will estimate the average effect at the patient level across the population (marginal models), accounting for clustering using GEE-type robust variance estimators and robust Poisson regression with an exchangeable working correlation matrix. All of the models generated for our healthcare utilization and missed occupational activities outcomes will include the same covariates as our analysis for patient health outcomes: age, sex, highest level of education achieved, income, duration of current episode of LBP, and Functional Comorbidity Index score (individual level), and primary care site rurality and number of active patients (cluster level). In the case of non-convergence or model instability, a possibility for any binary outcomes with very low or high event rates given our small number of clusters, we will attempt to model outcomes using an independence working correlation matrix. If we continue to experience issues with non-convergence or instability with alternate covariance structures, we will remove covariates, starting with duration of pain and income based on theoretical grounds and existing evidence on the strength of relationships between our covariates and our outcomes.

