Primary care physician or nurse practitioner visits will be presented as rates and compared using rate ratios with adjusted Poisson or negative binomial regression. Other healthcare utilization within the primary care team (whether there were any other consultations with interprofessional team members and whether or not there was group programming accessed), and healthcare utilization outside of the primary care team (medications, diagnostic imaging, walk-in clinic visits, ED visits, specialist physician visits, emergency department visits, hospital admissions, interventional procedures, surgeries, other health provider visits) will be presented as incidence rates and compared by calculating relative risks with confidence intervals using robust Poisson regression, accounting for clustering. These models will use time as an offset to account for variable follow-up times and will incorporate empirical covariance (“sandwich”) bias-adjusted (residual-based) estimators and the Fay and Graubard correction to account for small number of clusters. Time (days) lost from occupational activities (paid employment, volunteer, homemaking, or educational activities) and assistance required (hours of paid assistance, hours of unpaid assistance) due to LBP will be presented as rates and compared using rate ratios with negative binomial regression.

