therapies, spinal manipulation, massage, operant therapy, cognitive behavioural therapy, non-steroidal anti-inflammatory drugs, topical cayenne pepper, and multicomponent biopsychosocial care. Interventions that are recommended against include: traction, ultrasound, transcutaneous electrical nerve stimulation, and lumbar supports. Additionally, referrals for diagnostic imaging or physician specialist visits for spinal injections or surgery consultations are rarely needed for LBP and thus will be compared between arms for a potential reduction in low-value care. The intended implementation outcome is that patient participants receive care recommended in practice guidelines and do not receive care recommended against in practice guidelines, and that a low proportion of people receive *referrals or prescriptions* for diagnostic imaging, physician specialist, or medications outside of NSAIDs. Receipt of each intervention recommended by the guidelines, recommended against by the guidelines, and referrals (for imaging, spinal injections, or surgical consults) will be presented as incidence rates with confidence intervals and compared by calculating relative risks with confidence intervals using GEE-type robust variance estimates, accounting for clustering, using an exchangeable working correlation matrix. We will use empirical covariance (“sandwich”) bias-adjusted (residual-based) estimators and the Fay and Graubard correction to account for small number of clusters. We will incorporate the same covariates as with our effectiveness analysis.

5) Describing adherence to PT primary care recommendations. The intended implementation outcome is that patient participants report actioning the initial recommendations for physical activity and exercise and that those who were recommended to access PT services report doing so.

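### Does the time offset spoil the relative risks planned for yes/no healthcare-use outcomes?

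*Combined protocol and SAP*

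**What the plan says.** The section on healthcare utilization and missed occupational activity outcomes defines two within-team outcomes as "whether there were any other consultations with interprofessional team members and whether or not there was group programming accessed". These, together with a list of outside-team services, "will be presented as incidence rates and compared by calculating relative risks with confidence intervals using robust Poisson regression". The next sentence reads: "These models will use time as an offset to account for variable follow-up times". Time is not defined further.

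Under Health System and Societal Outcomes, the within-team outcomes are obtained "using data being collected from the EHR: consultations with other primary care team members". The outside-team outcomes come from the follow-up surveys, checked against the health record where possible.

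Physician or nurse practitioner visits, days lost and hours of assistance are handled separately, as rates compared by rate ratios.

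Elsewhere the plan compares yes/no outcomes by relative risk without mentioning an offset. One case is adverse events: "Any adverse events (yes/no) will be presented as incidence rates with confidence intervals and compared by calculating relative risks". Another is the process evaluation, where data collected "using the following data being collected from the EHR to describe the LBP management provided to patient participants in each arm" feed a comparison in which "referrals (for imaging, spinal injections, or surgical consults) will be presented as incidence rates with confidence intervals and compared by calculating relative risks".

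**The concern.** A relative risk compares proportions over the same period. With a log-time offset, a Poisson model of a 0/1 outcome compares proportions divided by mean time. If the arms are followed for different lengths of time, the result can move away from the ratio of observed proportions even when those proportions are equal, and a reader could take it for a 12-month relative risk.

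The source of the data adds to the doubt. Follow-up that varies between people most naturally describes survey attrition, but the two named outcomes come from the health record, which may be readable for the full year whether or not surveys are returned. Dividing full-year use by survey time would pair a numerator and a denominator from different windows.

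The outside-team outcomes are only listed. If they were counts, the offset would be right and the relative-risk label wrong.

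Healthcare use belongs to the second research question, and the plan is published so that analytic choices are fixed in advance.

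**Working it through.** The plan gives no figure on this point, so there is none to reproduce. The check asks how far the offset can move the result.

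**Inputs from the documents.** Follow-up is 12 months for everyone (Frequency and Duration of Follow-Up). Planned patient attrition is 20% overall, with no figure by arm (Sample Size and Power Calculations). Patient recruitment ended in November 2024 and data collection is planned to finish by December 19, 2025 (Trial Status). Someone enrolled on November 30, 2024 reaches 12 months on November 30, 2025, 19 days before that date. The calendar therefore cuts no one short, and variation in time should come mainly from attrition.

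**Assumptions not in the documents.** All drop-out is at month 3; the split by arm averages 20%; PT-led care loses more. Reversing the arms inverts the ratios.

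**Formula.** With arm as the only term and independence, the offset ratio is (ΣY₁/ΣT₁)/(ΣY₀/ΣT₀) = ratio of observed proportions × (mean T₀/mean T₁), where 1 is PT-led care. If a share f drops out at month 3, mean T = 0.25f + (1 − f) years. For 25% against 15%, the means are 0.8125 and 0.8875, and the factor is 0.8875/0.8125 = 1.092.

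For use seen only until drop-out, the observed proportion is f·p₃ + (1 − f)·p₁₂. Under a constant hazard, p₃ = 1 − (1 − p₁₂)^0.25. The ranges below run from p₁₂ = 0.12 (p₃ = 0.0315) to p₁₂ = 0.50 (p₃ = 0.159). The true ratio is 1.00 throughout.

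| Drop-out, PT-led / usual care | Mean time (years) | Full-year use, survey-time offset | Full-year use, no offset | Use seen to drop-out, offset | Use seen to drop-out, no offset |
|---|---|---|---|---|---|
| 20% / 20% | 0.850 / 0.850 | 1.000 | 1.000 | 1.000 | 1.000 |
| 22% / 18% | 0.835 / 0.865 | 1.036 | 1.000 | 1.001–1.004 | 0.966–0.969 |
| 25% / 15% | 0.8125 / 0.8875 | 1.092 | 1.000 | 1.002–1.009 | 0.917–0.924 |
| 30% / 10% | 0.775 / 0.925 | 1.194 | 1.000 | 1.003–1.019 | 0.841–0.854 |

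The same holds away from the null. With 12-month use of 60% in PT-led care against 40% in usual care (true ratio 1.50), and drop-out of 10% against 30%, the offset ratio is 1.486 and the ratio without it 1.774.

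**Reading the table by the meaning of time.**
- A common 12-month health-record window: T is the same for everyone, so the offset cancels.
- Each person's own observed record window: numerator and denominator match. The plan allows for the loss of two clusters, which could truncate some windows.
- Survey time for survey outcomes: the last two columns apply, and the offset is the better of the two under a constant hazard.
- Survey time for health-record outcomes: the 1.036 to 1.194 column applies, a pairing the plan does not state.

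**Outcome type.** The outside-team outcomes get relative risks from robust Poisson regression, while the outcomes that are clearly counts or durations get rate ratios. The same section anticipates non-convergence as "a possibility for any binary outcomes with very low or high event rates given our small number of clusters". Two of the references attached to the offset sentence are, by title, about binary outcomes in cluster trials. None of this is a definition, but yes/no is the natural reading.

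**The case for a change.** The strongest case for a change is that the estimand is left open. Offset or none, yes/no or count, record time or survey time could each be chosen after the data are seen, and a few lines of text would close the gap.

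Nor does the offset always help. If 71% of users had already appeared by month 3, the offset ratios for use seen to drop-out would be 1.023, 1.060 and 1.123 in the three unequal scenarios, against 0.988, 0.970 and 0.941 without it. Early use is conceivable in low back pain, but the documents give no timing.

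The plan also specifies covariates and an exchangeable working correlation, under which the simple factor does not carry over. Trials were simulated with 18 clusters of 63 and full-year use unrelated to the time offset. With losses of 10% in PT-led care and 30% in usual care, the mean factor was 0.96 at a working correlation of 0.02 and 1.20 at 0.05, against 0.84 from the formula. Even with equal expected follow-up, the offset and no-offset log estimates differed with a standard deviation of about 0.05 and 0.16 respectively.

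What stands is that time and outcome type are not spelled out and the label is loose. The simulated behaviour belongs to the mismatched pairing of full-year use with survey time, so it does not count against the offset where time is the window in which use was observed. The timing result shows a trade-off, not an error: the better choice depends on when use occurs. Silence about an offset in the process evaluation, a separate section, is not a contradiction.

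**Conclusion.** The concern does not call for a change to the plan. The description is accurate: an undefined time offset is applied to two outcomes worded as yes/no, and the result is called a relative risk. It would be too strong to say that this holds only when mean follow-up is equal. That is exact only for an unadjusted independence model judged against the ratio of observed proportions. Under a roughly constant hazard, the offset ratio stays close to the 12-month relative risk even when follow-up differs.

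No bias can be sized from the documents. With balanced attrition it is nil in the simple model. The 1.036 to 1.194 range rests on assumed arm differences in attrition, all at month 3, combined with survey time as the offset for health-record outcomes. Under the sensible readings, the offset either cancels or matches the observation window. For survey outcomes at a constant hazard, it leaves at most 1.019 in these scenarios, while removing it gives 0.841 to 0.969.

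What is left is detail that an analyst would ordinarily supply and report: take time as the window in which each source observed use, and describe the ratio accordingly. The primary outcome, physician and nurse practitioner visits, days lost, assistance and costs are not affected.

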#### Economic evaluation

We will estimate the cost-effectiveness of the PT-led care model from both a societal (primary) and health system payer (secondary) perspective to meet the needs of all knowledge users. The total costs will be determined by multiplying the quantity of resource use (or lost days) by the corresponding unit cost (or hourly wage), summing the total cost over each follow-up interval, and then calculating the mean cost at each follow-up time point, as well as an overall mean cost for the entire one-year study period. Results will be presented as aggregated and disaggregated costs. Utility data will be generated using EQ-5D-5L index values (ie. utility scores) from all follow-up assessment time points. We will estimate QALYs for every participant, using the area under the curve approach, assuming linear interpolation between the measurements. To accommodate the hierarchical structure of the data, we will use bivariate multilevel modeling to estimate the incremental cost-effectiveness ratio using a calculation of cost-per-QALY gained for PT-led primary care versus usual care and to estimate the incremental net benefit at various willingness to pay values. To account for clustering of study sites, as well as heterogeneity in costs and treatment effect across jurisdictions, we will model treatment group as

a fixed effect and the study site a random effect; adjusting for the same covariates as the primary analyses as fixed effects in our models. We will conduct a probabilistic sensitivity analysis using 10,000 Monte Carlo simulations to present the uncertainty in our cost-effectiveness estimates. Simulation results will be plotted on cost-effectiveness planes and we will generate cost-effectiveness acceptability curves to display the probability that the PT-led care model is cost-effective across a range of willingness to pay thresholds.

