### **Methods**

#### **Trial Design:**

The trial is a parallel arm cluster randomized controlled trial at 20 primary care sites randomized 1:1 to a PT-led or usual physician-led primary care model for LBP. Randomization of practices, rather than patient participants, allows evaluation of a model where PTs are able to fully integrate within the primary care team and reduces potential contamination between study arms. This protocol and analysis plan includes all of the items included in the Standard Protocol Items: Recommendations for Interventional Trial (SPIRIT) reporting guidelines. See Table 1 for a summary of the schedule of enrolment, interventions and assessments.

**Table 1.** Schedule of enrolment, interventions, and assessments.

	STUDY PERIOD							
	Enrolment of clusters	Allocation of clusters	Enrolment of patient participants	Post-allocation				Close-out
TIMEPOINT	Pre-intervention	Pre-intervention	0 (baseline)	6 wk	12 wk	6 mo.	9 mo.	12 mo.
ENROLMENT OF PRIMARY CARE SITES:								
Eligibility screen	X							
Informed consent	X							
Allocation to study group		X						
ENROLMENT OF PATIENT PARTICIPANTS:								
Eligibility screen			X					
Informed consent			X					
INTERVENTIONS:								
PT-led primary care				↔				↔

Usual care								
ASSESSMENTS:								
Participant characteristics and demographic information			X					
Participant health outcomes (RMDQ, pain intensity, EQ-5D-5L, PSEQ, PCS, TSK-11, PHQ-2)			X	X	X	X	X	X
Participant health and experience outcomes (Satisfaction, GROC, adverse events)				X	X	X	X	X
Health system and societal outcomes (provider encounters, EHR utilization, healthcare utilization, missed occupational activities, assistance required)				X	X	X	X	X
Implementation measures (timely access, PT as first point of contact, access to PT, LBP management)			X	X	X	X	X	X
Implementation measures (patient adherence)				X				
QUALITATIVE INVERVIEWS:								
Patient participants					X			
Primary care providers and leads, medical office assistants*							X	X

\* These interviews started 9 months after study launch.

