### **Frequency and Duration of Follow-Up:**

Patient characteristics and demographic information were collected at baseline. All patient-reported outcome measures are being collected at baseline, 6 weeks, and 3, 6, 9, and 12 months from the initial visit, with the primary comparison at 12 months. Patient satisfaction, global rating of change, adverse effects, and healthcare utilization are being collected at follow-up time points only. Patient adherence to PT recommendations is being collected at the 6-week follow-up.

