#### **Patient health and experience outcomes**

For our patient health outcomes, we will use linear mixed models to estimate individual patient participant outcomes adjusting for clustering by primary care centre. Our primary outcome (RMDQ) with repeated measures at baseline and the 6-week, 3-, 6-, 9-, and 12-month follow-up time points will be analyzed using linear mixed regression (using *PROC MIXED* in SAS), estimated using restricted

maximum likelihood (REML) estimation and a Kenward-Rogers degrees of freedom correction to account for a small number of clusters. The model will include fixed effects for time, intervention group by time interaction, (omitting the group main effect to ensure baseline differences are constrained to zero), factors used in the covariate-constrained allocation procedure (rurality of the cluster, number of active patients) and other pre-specified covariates associated with LBP-related disability (patient participant age, sex, income, highest level of education achieved, duration of current episode of LBP, Functional Comorbidity Index score). The correlation in repeated measures on the same participant will be modeled using a suitable covariance structure, identified using information criteria (AIC/BIC). To account for clustering within practices, site will be modeled as a random effect. The intervention effect will be obtained as the adjusted least square mean difference between arms at 12 months, with 95% confidence intervals. Secondary comparisons will be obtained using least square mean differences at intermediate time points.

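### The QALY rule names only follow-up visits as the source of utilities; followed literally, it covers weeks 6 to 52 against a full year of costs

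*Combined protocol and SAP*

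**What the plan says.** Three statements in the Economic evaluation section define the calculation.

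- Source of utilities: "Utility data will be generated using EQ-5D-5L index values (ie. utility scores) from all follow-up assessment time points".
- Construction of the QALY, for each participant: "using the area under the curve approach, assuming linear interpolation between the measurements". No start or end of the curve is given.
- Cost window: costs are summed over each follow-up interval and averaged, "as well as an overall mean cost for the entire one-year study period".

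Baseline utility is available. Frequency and Duration of Follow-Up says "All patient-reported outcome measures are being collected at baseline, 6 weeks, and 3, 6, 9, and 12 months from the initial visit", and the Table 1 row covering "RMDQ, pain intensity, EQ-5D-5L, PSEQ, PCS, TSK-11, PHQ-2" is marked at baseline as well as at every later visit. Under Research Questions, the second question asks about cost-effectiveness over one year.

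**The concern.** The plan treats baseline and follow-up as different things. Frequency and Duration of Follow-Up says of measures with no baseline value: "Patient satisfaction, global rating of change, adverse effects, and healthcare utilization are being collected at follow-up time points only". The primary model describes RMDQ "with repeated measures at baseline and the 6-week, 3-, 6-, 9-, and 12-month follow-up time points". The Costs paragraph under Health System and Societal Outcomes uses almost the same phrase as the utility sentence for self-reported expenses, which are not collected at baseline. The cost sentence in the Economic evaluation section also uses follow-up time points for quantities that exist only after baseline.

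If the utility sentence is read in the same sense, the first measurement is at week 6. Linear interpolation then has nothing to start from before week 6, so weeks 0 to 6 contribute no area. The costs of those weeks are still counted, including the PT's initial visit at which the brief intervention is given. Effect and cost would then run over different horizons in the same bivariate model, and neither the incremental net benefit nor the cost per QALY would answer the one-year question.

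**Working it through.** The plan states no utility, QALY or cost-per-QALY figure, so there is none to reproduce. The check works out the weight that each visit carries in the area under the curve.

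**Inputs.** Visits are at weeks 0, 6, 12, 26, 39 and 52. Table 1 labels the third visit 12 weeks and the text says 3 months, so week 13 was also tried. The cost window is 52 weeks.

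**Visit weights (trapezoid rule).** An interior visit has weight (next visit − previous visit) / (2 × 52). The first and last visits have half the adjacent interval, divided by 52.

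| Week | With baseline | Follow-up visits alone |
|---|---|---|
| 0 | 3/52 = 0.0577 | 0 |
| 6 | 6/52 = 0.1154 | 3/52 = 0.0577 |
| 12 | 10/52 = 0.1923 | 0.1923 |
| 26 | 13.5/52 = 0.2596 | 0.2596 |
| 39 | 13/52 = 0.2500 | 0.2500 |
| 52 | 6.5/52 = 0.1250 | 0.1250 |
| Sum | 52/52 = 1.000 year | 46/52 = 0.885 year |

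On the literal reading, a participant in full health all year would score 0.885 QALY.

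**Omitted incremental QALY.** Let d6 be the between-arm utility difference at week 6, and assume no difference at baseline. The missing piece is a triangle: 0.5 × (6/52) × d6 = 0.0577 × d6. For assumed d6 of 0.02, 0.05 and 0.10, this is 0.0012, 0.0029 and 0.0058 QALY.

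**Share of the one-year incremental QALY.** This depends on the course of the effect, which the documents do not give. All patterns below are assumptions. In the growing case, D is the week-52 difference; in the others, the week-6 difference is 1.

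- Grows linearly from zero to D at week 52: total 0.5 × D; omitted 0.5 × (6/52) × (6/52) × D = 0.0067 × D; share 1.3%.
- Constant from week 6: total 0.0577 + 0.8846 = 0.9423; share 0.0577/0.9423 = 6.1%.
- Peaks at week 6 and fades linearly to zero at week 52: total 0.0577 + 0.4423 = 0.5000; share 11.5%.
- Halves by the third visit and is zero by 6 months: total (3 + 4.5 + 3.5)/52 = 0.2115; share 27% (26% with a week-13 visit).
- Zero by the third visit: total 0.0577 + 0.0577 = 0.1154; share 50% (46% with a week-13 visit).

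**Effect on the economic results.** Incremental net benefit changes by 0.0577 × d6 × the willingness to pay. The plan names no willingness-to-pay value. At an assumed $50,000 per QALY and d6 from 0.02 to 0.10, the shift is about $58 to $288 per participant. When the QALY gain is positive, the cost-per-QALY ratio is multiplied by 1/(1 − share): 0.9423/0.8846 = 1.065 for a constant effect, 0.5000/0.4423 = 1.13 for a linear fade and 2 when half is lost. This factor acts on the size of the ratio; its direction follows the sign of the incremental cost.

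**Baseline imbalance.** Once time 0 is in the curve, a baseline utility difference b0 adds 0.0577 × b0 directly to the incremental QALY. The economic model takes the covariates of the primary analysis, and no covariate list in the plan includes the baseline EQ-5D-5L index.

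**The case against.** The best defence is that the utility sentence is loosely worded and that baseline was always meant to be the first point. It does not say that baseline is excluded. The authors do add a limiting word when they mean to exclude it, as in "healthcare utilization are being collected at follow-up time points only". The EQ-5D-5L index is designated for QALYs under the patient outcomes with no restriction on visits, baseline is one of the measurements to interpolate between, and a 46-week QALY would contradict the plan's own one-year question. This stands to the extent that a reader should not infer a deliberate decision to discard baseline. It does not remove the point. The sentence is the only one that says which visits supply the utilities, its natural reading in the plan's vocabulary leaves baseline out, and two analysts could produce 0.885-year and 1.0-year QALYs from the same data.

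Three further inferences go beyond the documents.

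- *That the cost per QALY is necessarily overstated.* This needs a positive incremental cost. The Process evaluation analysis section hypothesises reduced costs with PT-led care in all three STarT Back risk groups. With lower costs and a QALY gain, the ratio would become more negative.
- *That early benefit is lost altogether.* The week-6 value keeps weight 0.0577, half of its full weight. The loss is slight for a sustained or growing effect, and Duration of Treatment Period gives access to the PT for a year, so a purely early effect cannot be presumed.
- *That adding time 0 has no drawback.* Participants were recruited after cluster allocation, so baseline imbalance is possible. Unadjusted, it would enter with the same weight as the omitted week-6 term.

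**Conclusion.** Wrong as written, limited to the secondary economic objective; the primary RMDQ analysis is untouched. Followed literally, the rule produces a QALY over 0.885 year to set against one year of costs. The weights follow from the visit schedule alone. The omitted increment of 0.0577 × d6 also assumes equal baseline utility, and the 1.3% to 50% range rests on assumed effect patterns. The documents do not show which pattern is likely, which way the cost-per-QALY ratio would move, or that the authors intended to leave baseline out.

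**What to change.** In the Economic evaluation section, state that QALYs are the area under the EQ-5D-5L index curve from baseline (time 0) through 6 weeks and 3, 6, 9 and 12 months, so that utilities and costs cover the same 52 weeks. In the same place, add the baseline EQ-5D-5L index as a covariate in the QALY part of the bivariate model, so that baseline imbalance is not carried into the incremental QALY.

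The cost is one additional covariate and slightly more analysis work. The baseline index is already collected. The plan schedules analysis after data collection ends, so the change can be recorded beforehand through the amendment route that the plan describes.
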